therapy for TS patients. This paradigm is preferable to chronic stimulation for its potential to reduce stimulation-related side effects. Outcomes will be measured by comparing the results of chronic continuous stimulation (Specific Aim 1) to an acute test of responsive stimulation (Specific Aim 3). Responsive stimulation parameters will be identical to chronic continuous stimulation parameters and will strictly be within safety ranges. If acute responsive stimulation leads to low side effects and comparable clinical outcomes for a patient, we will test chronic responsive stimulation for one week at a time, up to four weeks in total. This procedure will be performed at an appropriate time point (approved by the Principal Investigator) after the 6 month primary endpoint is reached but prior to Month 36 (study completion) (see visits 6.1-6.4 in schedule of events). The patient programmer will allow patients to turn off responsive stimulation and switch back to standard continuous therapy. A firmware update from Medtronic will allow the Summit RC+S internal signal sensing and processing units to communicate with the stimulation unit. Outcomes for chronic responsive stimulation will also be measured by comparing the results of chronic continuous stimulation.

Duration of the Investigation: We expect the duration of this investigation will be five years. In the first year we plan to implant and follow the first two subjects. In Year 2 we will plan to implant and follow the third, fourth, and fifth subjects while we continue to follow the first two subjects. In Year 3 we plan to implant and follow the sixth and seventh, and eighth subjects while we continue to follow the first five subjects. In Year 4 we plan to implant and follow the ninth and tenth subject, but also to continue to follow the other eight subjects. In Year 5 we will complete follow-up

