Subjects will have a post-operative CT scan for lead location and to assess for intracranial air and hemorrhage. The CT scan will be fused back to the MRI. Each of the four contacts on each deep DBS lead will be measured, and localized on an atlas to confirm the correct lead position. In the future if an experimental fMRI or MRI is considered, FDA and IRB approval will be sought. The Summit system has not been evaluated for MR compatibility.

11) Specific Approaches for Specific Aim 1 Overview: The study will follow a prospective blinded design (see Figure 1 below). Effectiveness, tolerability, and safety will be assessed, and the study will allow for exploration of appropriate programming parameters.

12) Study Summary: Once subjects have been consented, baseline measures must be collected within two weeks of the surgery. Subjects will be followed with standardized measures for a minimum of 24 months (+/- 14 days) post-DBS implantation and a maximum of 36 months (+/- 14 days) post-DBS implantation for the research study. The main outcomes will be measured at 6 months post-DBS (+/-

14 days). There will then be three additional days of data collection where subjects will be either “on” DBS, “off DBS” or “on DBS responsive mode (Figure 1 and 2).” MRTRS scales will be collected in each mode for an independent video review. Stimulators will be blindly set to the “mode” for the day and left in that mode for one hour prior to data collection which will include MRTS and also physiology as recorded by the neurostimulator.

[figure not shown]

Figure 1. Study design

- Following recruitment and multidisciplinary screening, candidates will receive bilateral CM DBS plus bilateral ECOG strips, and bilateral chest implanted neurostimulators.
- Prior to implantation, primary outcome and secondary outcome variables will be assessed. A blinded videotape will be obtained of the MRTRS. The blinded videotapes will be evaluated by two blinded movement disorders neurologists who will score the MRTRS's at baseline and 6 months (+/- 14 days).
- Implantation will be accomplished by a neurosurgeon and neurologist, both of whom will not participate in the blinded evaluations of subjects.
- The primary effectiveness outcome for the study will be $\geq 40\%$ reduction on

the blindly rated YGTSS total motor/phonic tic sub-scale at six months on DBS as compared to pre-op baseline. The secondary effectiveness variable will be assessed by the MRTRS blinded ratings.

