- Physiology data beyond month 12, and the chronic stimulation titration (visits 6.1-6.4), may be performed at the participant’s home as necessary rather than at the University of Florida. The equipment used are all mobile as shown in the RC+S system configuration as explained in Section 18 (refer to Figure 3).
- Details of physiology collection procedure: The subject will be asked to put on EMG sensors and signals from this device will stream into the research host computer (RHC). The signals from the Summit RC+S device will also be downloaded onto the RHC, which will have the Summit Research

Development Kit (RDK) installed (refer to Section 19). Stimulation and brain activity data since the previous visit can then be reviewed and analyzed on an individual basis.

- The CM neurostimulators will be programmed in an outpatient setting to deliver only chronic continuous stimulation in all patients. Stimulation parameters will be adjusted as necessary to provide maximal tic reduction. The cortical strips will be chronically set to record mode for data collection only, until the acute Aim 3 responsive trial.
- The neurologist and DBS programmer will be allowed to adjust stimulation parameters during months 1-5 to achieve maximal tic suppression and minimal to no side effects. The programming that will be employed will be identical to that used for Parkinson's disease randomized trials[13, 67-71].
- At day 180 (6 months +/- 14 days), the primary and secondary outcome variables will be collected, as will all scales. If optimization is not achieved at Month 6, Month 6 data collection may be postponed as deemed necessary by the Principal Investigator (with the exception of the C-SSRS), up to 12 months (+/- 14 days) past the first programming visit (Month 1). However, there must be a 30 period of stable stimulation settings before primary outcomes are assessed.
- Primary and secondary outcomes and physiology collection will be assessed over approximately 3 outpatient days. The "on" DBS condition will be used and compared to the pre-operative baseline for the primary outcome (specific aim 1). The other conditions will be used for secondary analyses, and the on

responsive stimulation response will be compared to the pre-operative baseline (specific aim 3).

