binomial test. We will compare the baseline motor YGTSS to the on DBS condition at six months (primary outcome). We will also perform comparisons of baseline to on/off/responsive conditions, and also comparisons of on/off conditions at six months as secondary analyses. To compare on versus off condition, we will form paired difference scores of YGTSS (YGTSS on minus YGTSS off) at six months and test for significance using the Wilcoxon signed rank test.

Specific Analysis Approach for Aim 2: We will first investigate rate and pattern changes in physiology and the possible correlation with clinical manifestation of motor tics by using exploratory data analysis techniques that will be graphical in nature. These exploratory techniques will include spectrograms and event related potentials. We will then conduct a preliminary time series analysis estimating fractal dimension, line length, and area-under-the-curve of the raw signal. The data obtained from these analyses will inform subsequent analysis and guide the development of statistical methods to analyze these types of data streams. Subsequent analysis will be more comprehensive, and will include time-frequency analysis of specific frequency bands, measures of coherence between channels containing movement related activity, and quantification of phase-amplitude coupling between frequency bands of interest. Any of these techniques has the potential to identify candidate predictors of tic onset.

Specific Analysis Approach for Aim 3: This protocol calls for testing an acute responsive DBS condition in subjects who reveal physiological predictors that can be set to sense tic by ECOG, and to respond to tic on the CM implanted device. It may also be possible to both sense and deliver stimulation from the CM DBS lead. Data will be analyzed using the Wilcoxon signed rank test. **We will collect physiology**

data and analyze the data, and test chronic responsive stimulation settings one month at a time for those subjects that respond well to the acute testion after Month 3.

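### Aim 3 names no responsive-versus-off contrast, so benefit left over from months of continuous DBS could be read as a responsive effect

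*Combined protocol and SAP*

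**What the plan says.** **The comparator for responsive mode differs by section.**

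- Section 5, Specific Aim 3, uses continuous stimulation: "Outcomes will be measured by comparing the results of chronic continuous stimulation (Specific Aim 1) to an acute test of responsive stimulation". It then sets the step into chronic testing: "If acute responsive stimulation leads to low side effects and comparable clinical outcomes for a patient, we will test chronic responsive stimulation". No scale or margin defines comparable.
- Section 12, Details of the Protocol, uses the period before surgery: "responsive stimulation response will be compared to the pre-operative baseline (specific aim 3".
- Section 13, under Aim 1, lists: "We will also perform comparisons of baseline to on/off/responsive conditions, and also comparisons of on/off conditions at six months as secondary analyses".
- Section 13, under Aim 3, says only: "Data will be analyzed using the Wilcoxon signed rank test". It does not say which two conditions form the pair.
- Section 12, Specific Approaches for Aim 3, words the step into chronic testing as a favourable acute response, with no comparator.

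**How the acute test is run.** Section 12 says of programming: "The CM neurostimulators will be programmed in an outpatient setting to deliver only chronic continuous stimulation in all patients". Final settings must be unchanged for 30 days before the outcome. At Month 6 the device is set blind to on, off or responsive on separate days and "left in that mode for one hour prior to data collection which will include MRTS". Order is counterbalanced. The MRTRS videos from all three modes are scrambled and rated blind (sections 8 and 12), so the off ratings will exist.

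**The concern.** The acute test asks whether responsive stimulation does anything. A fair reference for that question has the same surgery, the same months of continuous stimulation and the same hour since the mode was changed. The off condition is that reference; baseline and continuous stimulation are not.

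If tic benefit outlasts stimulation by more than an hour, a responsive setting with no effect of its own will look better than baseline and closer to continuous stimulation. The baseline comparison has a second weakness. Section 4 describes a waxing and waning disease, and entry requires a high YGTSS (at least 35/50), so some change since baseline could occur without any stimulation.

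At stake is what an acute result can support. A comparable finding could reflect an effective responsive setting or residual benefit from continuous stimulation, and the named Aim 3 comparisons cannot tell the two apart.

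**Working it through.** **No stated figure to reproduce.** The plan gives no power, sample size or margin for Aim 3. Its only power calculation concerns Aim 1.

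**Inputs from the documents.** Ten implanted subjects (section 5). Responsive data only for those with a predictor (section 12), so n is at most 10 and the number is not stated. Wilcoxon signed rank, two-sided, 0.05 (section 13). One hour in each mode (section 12).

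**Assumptions, not in the documents.** A fraction c of the continuous effect E remains one hour after the switch. Responsive mode is inert. E is a 40% tic reduction, equal to 2 SD of the paired differences. Differences are normal with the same SD in every contrast. Non-significance stands in for comparable, because the plan gives no criterion.

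**Step 1: expected scores.** Let B be baseline and s the spontaneous fall since baseline.

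- On = B − s − E
- Off = B − s − cE
- Inert responsive = B − s − cE

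Hence baseline − responsive = s + cE, responsive − on = (1 − c)E, and off − responsive = 0. Carry-over moves the first two in the favourable direction. Spontaneous change moves only the first. The third is free of both.

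**Step 2: size for n = 10 and s = 0** (exact Wilcoxon null distribution, 20,000 simulated trials; true differences 2c SD, 2(1 − c) SD and 0).

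| c | Apparent reduction vs baseline | Gap to on | Responsive vs baseline significant | Responsive vs on not significant | Responsive vs off significant |
|---|---|---|---|---|---|
| 0 | 0% | 40% | 5% | 0% | 5% |
| 0.5 | 20% | 20% | 78% | 22% | 5% |
| 0.75 | 30% | 10% | 98% | 72% | 5% |
| 0.9 | 36% | 4% | >99% | 92% | 5% |

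With n = 6 and c = 0.5, 0.75 and 0.9, responsive versus baseline is significant in 35%, 66% and 80% of trials. Responsive versus on is non-significant in 65%, 89% and 96%.

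**Step 3: small numbers.** The smallest two-sided Wilcoxon p is 2/2^n: 0.0625 for n = 5, 0.031 for n = 6, 0.0078 for n = 8, 0.0020 for n = 10. With 5 or fewer subjects no contrast can reach 0.05, so responsive versus on would always be non-significant, whatever the truth.

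**Step 4: what the added contrast can detect.** Suppose responsive mode works as well as continuous stimulation. Then off − responsive = (1 − c)E = 2(1 − c) SD.

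| c | Difference | Power, n = 6 | n = 8 | n = 10 |
|---|---|---|---|---|
| 0 | 2.0 SD | 87% | 99% | about 100% |
| 0.5 | 1.0 SD | 35% | 61% | 78% |
| 0.75 | 0.5 SD | 11% | 19% | 28% |

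Carry-over therefore also hides a real responsive effect. On versus off has the same expected difference, (1 − c)E, which is why the two contrasts must be read together.

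**The case against.** The case on the other side has real substance.

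- **Off is not ignored.** On versus off is a planned contrast, and the Schedule of Events lists MRTRS ratings on, off and responsive from Month 1 onward. A reader might infer that the plan never tests responsive against off. The text does not support that: the Aim 3 Wilcoxon pair is unspecified, and part of the text next to the adaptive-control description in section 19 was not available. What stands is that the contrast is not named and that neither the Aim 3 analysis nor the comparable wording draws on off data.
- **It is a gate.** A reader might infer that an acute comparable result is declared a success for responsive DBS. Section 5 makes it a per-patient step into a longer chronic test, which an after-effect of an hour or so would not sustain. This stands. But that phase is again compared only with continuous stimulation, and its length differs between section 5 (weeks) and sections 8 and 12 (months), which must be reconciled.
- **The evidence may be wider than Month 6.** Responsive settings are also checked monthly. True, but no off comparator is named for those checks either.
- **Counterbalancing.** It balances order over the three test days. It cannot remove carry-over from earlier months that every subject shares.
- **Continuous stimulation is the natural comparator for an alternative, and Aim 3 is exploratory.** Both are fair. They argue for adding a contrast and keeping the existing ones.
- **Carry-over is assumed.** Correct; the documents give no value for it.

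**Conclusion.** The point holds as a gap in the Aim 3 analysis. Responsive mode is judged against two references that residual benefit would bias in its favour, while the reference with the same stimulation history is filmed and blindly rated but not named as a comparator.

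The size is conditional. Under the stated assumptions and n = 10, an inert setting would beat baseline in 5% of trials with no carry-over, 78% with half the benefit remaining and 98% with three quarters remaining. These figures show a range and do not estimate what will happen in this trial. The documents do not support saying that carry-over occurs, that any subject would be advanced because of it, or that Aim 3 as a whole would reach a wrong conclusion.

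A reader might also infer that each subject should have to score lower in responsive than in off before advancing. That does not follow. A single 0–20 rating with no margin would pass an inert setting by noise up to about half the time, and such a rule would change who receives chronic responsive stimulation.

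**What to change.** In section 13, Aim 3:

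1. Name responsive versus off at Month 6 on the blinded-video MRTRS (paired differences, Wilcoxon signed rank, each subject's difference shown) as an Aim 3 contrast, alongside responsive versus on and responsive versus baseline.
2. Read any comparable-to-continuous result together with on versus off on the same scale; section 13 writes the paired on–off difference for the YGTSS. Where on and off do not differ, report the acute comparison as uninformative about responsive efficacy. Judge this from the size of the differences, since a non-significant p-value in so few subjects is not evidence of equality.
3. State that fewer than 6 subjects with a predictor cannot reach two-sided p<0.05, so the contrast may be descriptive only.

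The investigators should reconcile the two wordings of the step into chronic testing (section 5 and section 12, Specific Approaches for Aim 3). No advancement rule is proposed here.

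**Cost.** Wording and one more secondary contrast; the videos and blinded ratings are already planned. Power is low, and carry-over in the off condition can mask a real responsive effect.

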(1) Test the hypothesis that centromedian (CM) continuous brain stimulation will be an effective and safe method for the treatment of tics in medication refractory TS. There is now a growing body of evidence supporting the use of DBS for tic suppression. Implantable brain stimulators provide a reversible and programmable solution to neuromodulation which are safer (no tissue destruction) and potentially more effective than ablative techniques such as thalamotomy, capsulotomy, and cingulotomy, especially because they can be performed bilaterally[62]. There are however important issues that may limit standard DBS effectiveness in this population including specific problems unique to this group of patients including the paroxysmal nature of the disorder. It would be desirable to design a therapy such as the one proposed in this grant application to neuromodulate only when needed (closed loop or responsive therapy). We plan to implant CM

thalamus and cortical ECOG bilaterally in 10 medication refractory TS subjects. We will employ a prospective blinded staggered onset design. We hypothesize that by using a chronic (continuous) stimulation strategy we will be able to achieve a greater than 40% reduction (over 6 months) in total tics (motor and phonic on the YGTSS) in more than $\frac{1}{2}$ of our subjects (6/10). We will in this study assess safety and also employ stopping rules to ensure subject safety.

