and data analysis and submit publications for peer review. These time estimations are plans that could be subject to change based on a number of external factors that may be out of our control. We plan to follow each subject clinically for a minimum of 24 months following implant, and to follow them for 12 more months for a minimum of 2 and a maximum of 4 research visits, and then clinically each year as long as they wish to remain implanted, and to assess needs for battery replacement. We plan to apply to CMS and Medicare for insurance coverage of the device implantation and battery replacement costs, and to apply to Medtronic for device donation (Medtronic has already reviewed this proposal in their scientific grants committee and approved donation of the devices and replacement devices).

6) Protocol: Methodology to be used - The study will be a prospective blinded design. Subjects will include ten individuals with medication refractory and severely disabling TS. We expect to consent and screen 50 individuals in order to enroll ten. A total of 6/10 subjects (60%) will need to be “responders” as a result of the intervention (YGTSS motor tic subscale reduction of $\geq 40\%$) for this study to reach effectiveness criteria.

Inclusion Criteria

- The diagnosis of TS must be made by both a fellowship-trained movement disorders neurologist and a psychiatrist and must meet Diagnostic and Statistical Manual of Mental Disorders (DSM-V) criteria for a diagnosis of TS.
- Yale Global Tic Severity Scale (YGTSS; 100) must be $\geq 35/50$ for at least 12 months and the motor tic subscore ≥ 15 . The TS must be causing incapacitation with severe distress, self-injurious behavior, and/or quality of life disruption.

OCD, Depression, and ADHD are not exclusionary[63-65] provided tics are the major difficulty requiring surgical intervention.

- There are no gender criteria for this study.

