Power Analysis: We will determine the effectiveness of DBS by comparing total tic score (YGTSS) at the six month time point to the pre-operative value for each subject. A 40% or greater reduction will be considered a successful response. The power to detect a statistical significance between a null proportion of 0.10 (this assumes that the true proportion of successful responders is 10%). The power analysis revealed that for an alternative proportion of .60 (i.e., 6 of 10 patients will show a

40% or greater reduction in motor tics at six months) there is a statistical power of 0.80 at an alpha level of .05. Therefore, we anticipate ten participants will be required for this study. The *power* procedure in Statistical Analysis Software (SAS), version 9.1 was used to conduct the power analysis. Data collected from this study will provide additional and currently unavailable data to inform power analysis of subsequent studies in Table 2 below.

Table 2. Power Analysis for Sample Size Effects

Table Power Analysis		Sample Size					
		8 patients		9 patients		10 patients	
Alternative proportion	Number of responders	Power	Number of responders	Power	Number of responders	Power	
.30	2	0.25	3	0.27	3	0.29	
.40	3	0.39	4	0.43	4	0.46	
.50	4	0.54	5	0.59	5	0.63	
.60	5	0.70	5	0.75	6	0.80	

General Analysis Approaches: The Wilcoxon signed rank test will be used to test for significant pre-post changes in numerical measures (e.g., YGTSS). Spearman correlations will be used to test relationships among numerical measures (e.g., neurocognitive measures, severity of tics and quality of life measures). Both the Wilcoxon signed rank and Spearman correlation tests are nonparametric procedures that are robust from data departures from normality and appropriate in the case of small sample sizes. All statistical tests will be two-sided and will be considered significant if p-values are less than 0.05. SAS software will be used to conduct all data analysis.

Specific Analysis Approach for Aim 1: We will determine the effectiveness of the “on condition” of DBS by comparing motor tic score (YGTSS) at the six month evaluation to the pre-operative value for each subject. A 40% or greater reduction will be considered a successful response. We will then test the hypothesis that the proportion of successful responders is greater or equal to (6/10) using the exact

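### The power of 0.80 that justifies ten subjects fits neither the 6-of-10 effectiveness rule (63% at a true rate of 0.60) nor a one-sample exact test against 0.10 (94.5%)

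*Combined protocol and SAP*

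**What the plan says.** **The success rule.** Section 6 (Protocol) states: "A total of 6/10 subjects (60%) will need to be" responders "for this study to reach effectiveness criteria". Section 5 (Purpose), aim 1, hypothesises the required reduction in more than half "of our subjects (6/10").

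**The sample-size argument.** Section 13, Power Analysis, defines a responder: "A 40% or greater reduction will be considered a successful response". It sets a null proportion of 0.10 and says that "for an alternative proportion of .60 (i.e., 6 of 10 patients will show a" reduction of that size, "there is a statistical power of 0.80 at an alpha level of .05". It concludes: "Therefore, we anticipate ten participants will be required for this study". Table 2 has a column for the number of responders and a column for power; at .60 with ten patients it shows 6 and 0.80. The only source named is the SAS power procedure.

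**The planned test.** Section 13, Specific Analysis Approach for Aim 1, names an exact binomial test but words its hypothesis around 6/10, not 0.10. General Analysis Approaches makes all tests two-sided at 0.05.

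The probability of meeting the 6/10 rule is not given anywhere.

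**The concern.** The figure 6/10 does two jobs. In section 6 it is an observed count that must be reached. In section 13 it restates an assumed true proportion of .60. If the bar is set at the number of responders expected under the alternative, a treatment that performs exactly as assumed will clear it well under 80% of the time.

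What is at stake is how the result is read. Ten people receive bilateral intracranial implants, and the study is judged on a count whose operating characteristics are unstated. The one probability offered, 0.80, invites use as the chance of success. Nor does the plan say what will be reported for 4 or 5 responders, a likely outcome under the design assumption.

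**Working it through.** **Inputs.** n = 10, single arm (sections 6 and 13); rule X ≥ 6 (section 6); null 0.10, alternative 0.60, alpha .05, stated power 0.80 (section 13). Assumed: all ten evaluable, independent, and one responder definition throughout. X is then Binomial(10, p).

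**1. Reproducing the stated 0.80.** The formula that matches is a one-sided comparison of two independent proportions with n per group and pooled variance under the null:

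power = Φ{[(p1 − p0)√n − 1.645·√(2·p̄(1 − p̄))] / √(p0(1 − p0) + p1(1 − p1))}

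With p0 = 0.10, p1 = 0.60, p̄ = 0.35 and n = 10:

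- 0.50 × √10 = 1.581
- 1.645 × √0.455 = 1.110
- √(0.09 + 0.24) = 0.574
- (1.581 − 1.110)/0.574 = 0.82, so power = 0.794

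The same formula across Table 2 (printed value in brackets):

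| Alternative | n = 8 | n = 9 | n = 10 |
|---|---|---|---|
| .30 | 0.253 (0.25) | 0.273 (0.27) | 0.293 (0.29) |
| .40 | 0.391 (0.39) | 0.426 (0.43) | 0.459 (0.46) |
| .50 | 0.545 (0.54) | 0.591 (0.59) | 0.633 (0.63) |
| .60 | 0.702 (0.70) | 0.752 (0.75) | 0.794 (0.80) |

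All twelve cells agree to within 0.01. The source is inferred from this match; the protocol does not state it. One-sample normal approximations give 0.83 to 0.99 for the headline cell, and the one-sample arcsine gives 0.95 to 0.97.

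**2. The 6/10 rule.** At p = 0.60:

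P(X ≥ 6) = 0.2508 + 0.2150 + 0.1209 + 0.0403 + 0.0060 = 0.633

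The chance of missing the criterion is therefore 0.367. (The 0.63 in Table 2 at .50 with ten patients is a coincidence.) At other true rates:

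| True rate | P(X ≥ 6) |
|---|---|
| 0.10 | 0.00015 |
| 0.50 | 0.377 |
| 0.60 | 0.633 |
| 0.65 | 0.751 |
| 0.673 | 0.80 |
| 0.70 | 0.850 |

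**3. The exact test against 0.10.** P(X ≥ 3 | 0.10) = 0.070, which is too large. P(X ≥ 4 | 0.10) = 0.0128, which is below both 0.05 and 0.025, so rejection starts at 4 responders whether the test is one-sided or two-sided. Power at 0.60 is P(X ≥ 4) = 0.945.

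**4. Does any count threshold give 0.80?** At p = 0.60, X ≥ 4 gives 0.945, X ≥ 5 gives 0.834 and X ≥ 6 gives 0.633. None gives 0.80.

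**5. The zone between test and rule.** At p = 0.60, P(X = 4) + P(X = 5) = 0.1115 + 0.2007 = 0.312. Upper-tail p-values against 0.10 are 0.0128 for 4/10 and 0.0016 for 5/10. Exact 95% intervals are 0.122 to 0.738 and 0.187 to 0.813.

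**6. The responder column of Table 2.** The entries are n × p, rounded: 8 × .30 = 2.4, shown as 2; 9 × .60 = 5.4, shown as 5; 10 × .60 = 6. They are expected counts, not thresholds.

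**7. Sensitivity to a missing subject.** If one of the ten is missing and counted as a non-responder, P(at least 6 of the other 9 | 0.60) = 0.483.

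**The case against.** The best defence is that section 13 presents 0.80 as power against a 0.10 null, not as the chance of 6/10. A reader might infer that the protocol promises an 80% chance of meeting its criterion; it makes no such statement, and that charge should not be laid. The responder column also reads naturally as an expected count, since its 3 responders at .30 could hardly be a success threshold. This stands, but it does not rescue 0.80, which is not the power of a one-sample exact test against 0.10 either.

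A reader might also infer that 4 or 5 responders would force two opposite conclusions. The documents do not support that. Exceeding 10% and falling short of 6/10 are compatible statements, and an effectiveness bar above the significance boundary is a legitimate choice. Moreover, the Aim 1 text words the exact test around 6/10, so a test against 0.10 is not yet what that section specifies. Any reporting rule that relies on the 10% null must wait until the null is confirmed.

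Finally, section 6 defines response on the motor subscale, sections 5, 7 and 12 use total tics, and section 13 uses both. Applying .60 to the section 6 rule assumes that one definition governs.

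**Conclusion.** The concern holds in a limited form. The only figure that justifies ten subjects is not a property of this single-arm design. It is 17 points above the chance of meeting the declared criterion at the design alternative (0.80 against 0.633) and about 14 points below the power of the one-sample exact test against 0.10 (0.945). Correcting the power calculation alone would leave the criterion at 0.633 and widen the gap between reported power and chance of declared success to 31 points.

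The 0.633 rests on ten evaluable, independent subjects and a single responder definition; section 13 gives no dropout allowance, and counting losses as non-responders would lower it. The 0.945 applies only if 0.10 is the null of the exact test. The two-group origin of 0.80 is an inference. None of this shows that ten subjects or the 6/10 bar is a wrong choice.

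**What to change.** Keep ten subjects and the 6/10 rule, and revise section 13 as follows.

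- Replace 0.80 and the Table 2 powers with figures for the actual design. For the 6/10 rule: 63% at a true responder rate of 0.60, 80% only at about 0.67, and 0.015% at 0.10. If the exact test is run against 0.10: rejection at 4 or more of 10, with power 0.945 at 0.60.
- Describe .60 as the assumed true proportion, and head the Table 2 column *expected number of responders*.
- State the assumptions behind these figures: ten evaluable subjects and one named responder definition.
- Confirm the null of the Aim 1 exact test. If it is 0.10, state in advance that 4 or 5 responders will be reported as *exceeds the 10% null, effectiveness criterion not met*, with the exact 95% interval (4/10: 12% to 74%; 5/10: 19% to 81%).

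This changes text and one table, with no added patients or visits. The price is that the stated chance of meeting the effectiveness criterion at the hypothesised rate becomes 63%, less favourable than the 0.80 now printed.
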